#### 5.2 Study Sample Size

For the purposes of sample size calculation the following assumptions have been made:

- estimates of intra-subject variability (CVw) of 50% and 40% for Cmax and AUC(0-last), respectively. Data obtained from previous food effect study (QCL117415, data on file)
- two one-sided tests with a probability of type 1 error of 0.05 for PK endpoints Cmax and AUC(0-last), ie 90% CI to be calculated
- acceptance interval of 70.00% to 143.00%
- 80% power assuming the true ratio is between 95.00% and 105.00%

#### Part 1

Based on the above assumptions, 40 subjects are to be dosed to achieve 34 evaluable subjects for Cmax (PK parameter with highest CVw value).

It should be noted that 34 subjects are required for each comparison of interest and therefore replacement subjects may be utilised, see Section 5.3 for further details.

#### Part 2

Based on the above assumptions, 38 subjects are to be dosed to achieve 34 evaluable subjects for Cmax (PK parameter with highest CVw value).

#### 5.3 Randomisation (including Replacement Subjects)

This study is non-randomised.

#### Part 1

Subject numbers will be allocated on the morning of first dose of IMP dosing according to the code 001 to 040 using the lowest number available. If required, replacement subjects will be allocated subject numbers 901 to 940, where the last 2 digits are the same as those of the original subject (eg if Subject 005 withdraws, the replacement will have Subject Number 905 and will receive the reference treatment, as well as IMP/NIMP for at least one treatment period not already received by the replaced subject).

It is not anticipated that replacement subjects will be used in this study; however, in the event that a replacement will be required, this will be discussed with the investigator and sponsor. If replacement of subjects is invoked, up to 4 additional subjects may be enrolled in Part 1 of the study in order to achieve sufficient evaluable subjects per relevant comparison; the maximum number of subjects that may be dosed is 44. Any subject withdrawn due to an IMP or NIMP-related AE or termination of the study will not be replaced. Subjects withdrawing for other reasons may be replaced at the discretion of the investigator and sponsor to ensure sufficient evaluable subjects. Any replacement subject will be required to complete the reference treatment period (Period 1) in addition to any further test periods (Periods 2 to 4) not already completed by the replaced subject.

#### Part 2

Subject numbers will be allocated on the morning of first dose of IMP dosing according to the code 201 to 238 using the lowest number available. If required, replacement subjects will be allocated subject numbers 801 to 838, where the last 2 digits are the same as those of the original subject (eg if Subject 205 withdraws, the replacement will have Subject Number 805 and will receive the reference treatment (Period 1), as well as the IMP/NIMP for Period 2).

It is not anticipated that replacement subjects will be used in this study; however, in the event that a replacement will be required, this will be discussed with the investigator and sponsor. If replacement of subjects is invoked, up to 4 additional subjects may be enrolled in Part 2 of the study in order to achieve sufficient evaluable subjects per relevant comparison; the maximum number of subjects that may be dosed is 42. Any subject withdrawn due to an IMP or NIMP-related AE or termination of the study will not be replaced. Subjects withdrawing for other reasons may be replaced at the discretion of the investigator and sponsor to ensure sufficient evaluable subjects. Any replacement subject will be required to complete the reference treatment period (Period 1) in addition to Period 2.

#### 5.4 Blinding Issues

This is an open-label, non-randomised study and therefore blinding is not required.

### 6 **Populations for Analysis**

#### 6.1 Safety Population

The safety populations for each of Parts 1 and 2 will include all subjects who have received at least 1 dose of study drug (ie KD025, itraconazole, rabeprazole, rifampicin or omeprazole) in that study part.

The safety populations will be confirmed by Quotient with approval from Kadmon after database lock and will be used for the analysis of demographic and baseline characteristics, and all safety variables.

#### 6.2 Pharmacokinetic Population

The PK population will be defined separately for Part 1 and Part 2 and will include all subjects who have received at least one dose of IMP and who have a minimum of 1 valid post-dose analytical result for PK parameter estimation and who satisfy the following criteria for at least one profile:

- no missing samples at critical time points eg around the Cmax
- no relevant protocol deviations which may impact the study objectives with respect to the PK endpoints and may include any dosing deviations relating to IMP or NIMP
- no relevant AEs such as vomiting which suggest that the dose was not absorbed for a particular subject

The PK populations will be confirmed by Quotient with approval from Kadmon following derivation of all PK parameter estimates.

All subjects will be used for the PK data listings and the PK population will be used for the provision of PK summary statistics, summary tables and figures.

If required, PK analysis datasets will be documented by Quotient with approval from Kadmon at the same time as the PK population. The PK analysis datasets will be a subset of the relevant PK population and will include subjects with sufficient valid PK profiles and who have completed both the test and reference periods for the following pairwise treatment comparisons (test versus reference) to be made ie one PK dataset per comparison):

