11.3 Dosing Compliance

During all clinical phases of the study, subjects will be observed by study staff to assure compliance to all study procedures, including dose administration.

Mouth and hand checks will be conducted after dosing to ensure the tablet/capsule has been swallowed.

When NIMP is taken at home, subjects will record the time of administration in a diary card.

The date and time that each subject is dosed will be recorded in the subject's source data. Any violation of compliance will require evaluation by the investigator and sponsor to determine if the subject can continue in the study.

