#### Part 2

 KD025 200 mg BID + omeprazole (Period 2) vs KD025 200 mg BID alone (Period 1) ie PK Dataset 4

In addition, any dosing deviations relating to any of the NIMPs will be reviewed to assess potential impact on the study objectives ie if a subject has not received all NIMP doses then they may be excluded from the relevant PK analysis dataset.

The PK analysis dataset(s) may be used to generate additional summary tables and figures for the PK concentration and PK parameter data and will be used for the formal statistical analysis of the PK parameter data.

Requirements for additional summary tables and figures will be documented at the same time as the PK population.

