#### Part 2

• KD025 200 mg BID + omeprazole (Period 2) vs KD025 200 mg BID alone (Period 1)

Only subjects who complete both the test and reference treatments within the relevant periods will be included in the statistical analysis. Furthermore for AUC(0-inf) only, a subject must have reliable estimates of AUC(0-inf) for both test and reference treatments within the relative periods to be included in the statistical analysis. If the number of subjects with reliable estimates for both periods is less than 17 (ie less than 50% of planned number of evaluable subjects) then no formal statistical analysis of AUC(0-inf) will be performed ie descriptive summaries only.

The adjusted means including differences from the pairwise comparisons and their associated 90% CIs obtained from the model will be back transformed on the log scale to obtain adjusted geometric mean ratios (GMRs) and 90% confidence intervals (CIs) of the ratios.

In addition, 2 one-sided tests will be performed to obtain the p-value for the test of the null hypothesis of non-equivalence. The one-sided tests will test the following hypotheses against the log transformed lower and upper limits of the equivalence acceptance range.

- Test against the lower limit
  - $H_{01}$ :  $\mu_T \mu_R < \ln(0.7)$
  - $H_{11}$ :  $\mu_T \mu_R \ge \ln(0.7)$
- Test against the upper limit
  - $H_{02}$ :  $\mu_T \mu_R > \ln(1.43)$
  - $H_{12}$ :  $\mu_T \mu_R \le \ln(1.43)$

where H01 and H02 are the null hypothesis (ie test and reference not bioequivalent) for the lower and upper limits respectively and H11 and H12 are the alternative hypothesis (ie test and reference are bioequivalent) for the lower and upper limits respectively.  $\mu_T - \mu_R$ is the difference of the log transformed mean values for test and reference. Each one-sided test will be performed at a 5% significance level ie a p-value of less than 5% indicates there is evidence to reject the null hypothesis of non-equivalence.

Adjusted GMRs and 90% CIs for the adjusted GMRs for the pairwise treatment comparisons listed above, where the ratio is defined as test/reference will be presented. In addition, the largest p-value from the 2 one-sided tests and the intra-subject variability values (denoted as CVw in the results table(s)) will also be presented.

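### SAP 6.2 leaves it optional whether a subject with an incomplete run-in stays in the interaction analysis, and has that settled with sponsor approval after all PK parameters are known

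*SAP*

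**What the plan says.** Four statements in SAP 6.2 work together.

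- **Timing and approver of the PK population:** "The PK populations will be confirmed by Quotient with approval from Kadmon following derivation of all PK parameter estimates".
- **Timing and approver of the analysis datasets:** "If required, PK analysis datasets will be documented by Quotient with approval from Kadmon at the same time as the PK population".
- **Rule for an incomplete run-in:** "if a subject has not received all NIMP doses then they may be excluded from the relevant PK analysis dataset". This stands at the end of the section, under Part 2, but is worded for all the NIMPs. It gives no number of doses and no critical days.
- **Use of the datasets:** they "will be used for the formal statistical analysis of the PK parameter data".

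The PK population criteria do not settle the matter earlier. They exclude relevant protocol deviations, which "and may include any dosing deviations relating to IMP or NIMP", without defining relevant. A subject also qualifies if he is one "who satisfy the following criteria for at least one profile", so a poor run-in in one test period does not by itself remove him. The dataset rule decides.

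SAP 9.2.4 adds: "Only subjects who complete both the test and reference treatments within the relevant periods will be included in the statistical analysis". It does not say whether completing a treatment means taking every run-in dose.

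On home dosing, Protocol 11.3 says: "When NIMP is taken at home, subjects will record the time of administration in a diary card".

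**The concern.** Run-in adherence, IMP or NIMP dosing deviations and vomiting can all be judged from the dosing, diary, meal and adverse event records. Only missing samples around Cmax and the reliability of a derived parameter need PK output. The SAP nevertheless puts both kinds of decision at one point, after derivation. An exclusion for a missed dose can then be correlated with the ratio it removes, whether or not anyone intends it.

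Exposure to the problem is not negligible. From the schedule in Protocol 8.1 and Appendices 2 and 3, the run-in doses taken at home are 5 of 7 for itraconazole, 5 of 6 for rabeprazole, 6 of 9 for rifampicin and 2 of 3 for omeprazole, which is 18 of 25. The documents give no missed-dose rate.

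At stake are the conclusion of no effect, drawn when the 90% CIs lie within 70.00% to 143.00%, and the size of the reported GMR.

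**Working it through.** **Inputs.** Protocol 15.1 and SAP 5.2 give CVw 50% (Cmax) and 40% (AUC(0-last)), limits 0.70 to 1.43, two one-sided tests at 5%, 80% power at a true ratio of 0.95 to 1.05, and 34 evaluable subjects from 40 dosed (Part 1) or 38 (Part 2). Assumed, because the documents give no figure: 37 completers, the number of deviators, and the effect of a missed dose.

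**The plan's own figure.** The within-subject SD on the log scale is √ln(1 + 0.5²) = 0.472. The SD of a paired log ratio is 0.472 × √2 = 0.668. Exact power with n = 34 is 80.1% at a ratio of 0.95 and 80.6% at 1.05 (33 df), and 34 is the smallest n that reaches 80%. The sample size reproduces.

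**What is needed to pass.** With n = 37, SE = 0.668/√37 = 0.110 and t(0.95, 36 df) = 1.688. For a typical variance the observed GMR must be at least 0.70 × exp(1.688 × 0.110) = 0.84.

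**Selection, Cmax alone.** I simulated 40,000 trials per setting with 37 completers. Selection means dropping the lowest k ratios among the deviators, for k from none to all, and counting a pass if any choice passes. Two extremes were taken for the missed doses: no effect, or full removal of the interaction (deviators' true ratio 1). Chance of passing at a true ratio of 0.70:

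| Deviators | Missed doses | Keep all | Exclude all | Choose after seeing ratios |
|---|---|---|---|---|
| 2 | no effect | 5.0% | 4.9% | 6.3% |
| 3 | no effect | 5.0% | 5.1% | 7.5% |
| 5 | no effect | 5.0% | 4.8% | 9.3% |
| 5 | interaction removed | 10.7% | 4.9% | 13.6% |

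In the last row, keeping all five moves the average ratio to 0.70^(32/37) = 0.73, so much of the rise comes from dilution rather than from seeing the results. At a true ratio of 0.80 with five harmless deviators, the pass rate goes from 32% to 44%.

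**Several parameters together.** With Cmax and one AUC (CVw 40%) both at 0.70 and an assumed correlation of 0.8, the joint false-conclusion rate is about 2.5%. It rises to about 5% with five harmless deviators and to about 4% with three.

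**Large effects.** At a true ratio of 0.5 or 0.2 the pass rate is zero to four decimals, with or without selection.

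**Effect on the estimate.** The two lowest of five standard normal values average −1.163 and −0.495. Dropping those two subjects from 37 shifts the mean log ratio by 0.668 × (1.163 + 0.495)/35 = 0.032, so the GMR is multiplied by 1.032.

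**The case against.** The case for leaving the plan alone has substance.

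- **Disclosure.** Exclusion reasons are tabulated and listed (SAP 7.3, 7.4), deviations are listed (7.2), NIMP compliance is summarised and dosing times are listed (10.2), and PK parameters are listed for all subjects (6.2, 9.2.3). A reader could rebuild the analysis of all completers. That stands, but it allows detection afterwards and does not fix the main analysis in advance.
- **Criteria signed before lock.** Protocol 15.4 requires this. The criterion signed for run-in doses is itself optional, so the signature does not bind the choice.
- **Supervised doses.** The doses nearest KD025 are taken in the clinic for itraconazole (Days -1, 1 and 2), rifampicin (Day -1), and rabeprazole and omeprazole (Day 1), and Protocol 11.3 provides mouth and hand checks. This makes a full loss of the interaction less likely and favours the smaller figures.
- **Case-by-case review.** A reader might infer that any missed dose should mean exclusion. The documents do not support that. SAP 6.2 asks for a review of potential impact. Protocol 6.2.2 to 6.2.4 describe 4 days of itraconazole as common practice, near-maximal rabeprazole effect after one dose, and steady-state induction with 5 to 9 days of rifampicin. Automatic exclusion could also erode the 34 evaluable subjects. This part of the objection stands in full.

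**Conclusion.** The point holds as one of timing and discretion. SAP 6.2 permits an optional, sponsor-approved choice on run-in deviators after their ratios are known, and the chosen set feeds the formal GMR and CI. None of the safeguards above removes that choice, and no analysis of all subjects with both profiles is planned as a check.

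For Cmax alone at a true ratio of 0.70, one-sided use could raise a false no-effect conclusion from about 5% to 6% to 7.5% with two or three harmless deviators, about 9% with five, and about 14% with five whose interaction was removed. These figures rest on assumed numbers of deviators and on selection always in one direction.

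A reader might infer that the test's 5% error is simply lost. The documents do not support so broad a statement. The decision rule needs three parent parameters to pass. With only two modelled, five harmless deviators bring the joint rate to about 5%. At a correlation of 0.9 the joint rate with five is about 6%, and if only Cmax is affected the single-parameter figures are closer. For an effect as large as the preliminary 80% decrease with rabeprazole (Protocol 6.1), the verdict cannot change and only the estimate can. The risk lies mainly near a limit. Omeprazole is the candidate, since Protocol 6.1 expects it to interact more weakly.

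Nor do the documents show that selection took place. They show only that it is possible.

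**What to change.** Split the decision in SAP 6.2.

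1. Before concentrations or PK parameters reach the staff who decide, document from the dosing, diary, meal and adverse event listings which subject-periods are out for IMP or NIMP dosing deviations or vomiting. Use a criterion for each NIMP that the sponsor and investigator set in advance, and define completion in SAP 9.2.4 in the same terms. The cut-off is theirs to choose.
2. After PK derivation, allow exclusions only for missing critical samples or unreliable parameters.
3. Report the GMR and 90% CI for all subjects with both profiles as a sensitivity analysis.

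The cost is SAP wording, one earlier sign-off and one repeat model per comparison.

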#### Part 1

- KD025 200 mg QD + itraconazole (Period 2) vs KD025 200 mg QD alone (Period 1) ie PK Dataset 1
- KD025 200 mg QD + rabeprazole (Period 3) vs KD025 200 mg QD alone (Period 1) ie PK Dataset 2
- KD025 200 mg QD + rifampicin (Period 4) vs KD025 200 mg QD alone (Period 1) ie PK Dataset 3

#### Part 2

 KD025 200 mg BID + omeprazole (Period 2) vs KD025 200 mg BID alone (Period 1) ie PK Dataset 4

In addition, any dosing deviations relating to any of the NIMPs will be reviewed to assess potential impact on the study objectives ie if a subject has not received all NIMP doses then they may be excluded from the relevant PK analysis dataset.

The PK analysis dataset(s) may be used to generate additional summary tables and figures for the PK concentration and PK parameter data and will be used for the formal statistical analysis of the PK parameter data.

Requirements for additional summary tables and figures will be documented at the same time as the PK population.

## 7 Subject Disposition, Demographics and Baseline Characteristics

No formal statistical testing will be performed on subject disposition, or on demographic or baseline data. Summaries of subject disposition and analyses populations will be based on all subjects and summaries of all other data described in this section will be based on the safety population, unless otherwise stated.

Separate summary tables and listings will be produced for each study part.

If the PK analysis datasets differ from the safety populations, demographic and baseline data summaries may also be produced for the PK datasets.

#### 7.1 Screening Failures

Data for subjects who have failed screening will not be databased and therefore will not be included in any analyses or any of the tables, figures or data listings.

#### 7.2 Subject Disposition and Withdrawals

The number and percentage of subjects enrolled, dosed (overall and in each period), completed and discontinued will be presented overall. If any subjects discontinued from

Reporting and Analysis Plan KD025-107 (QSC200311) Final v2.0 09 Nov 2018 Page 19 of 99 the study early then the number of subjects for each reason for discontinuation will be presented overall. However, if none of the subjects discontinued from the study early, then the reasons for discontinuation will not be populated in the summary table.

Subject disposition and withdrawal data will be listed including details of informed consent.

Protocol deviations and any violations of the inclusion/exclusion criteria will also be listed.

#### 7.3 Analysis Populations

A summary table will be produced detailing the number and percentage of subjects in each analysis population presented overall. The reasons for exclusion from each population will also be included in the summary.

Details of subjects included and excluded in the different analysis populations will be listed.

#### 7.4 Analysis Datasets

If applicable, a summary table will be produced detailing the number and percentage of subjects in each PK analysis dataset presented by treatment. The tables will be based on the relevant population the dataset is a subset of (ie the PK population). The reasons for exclusion from each dataset will also be included in the summary.

Details of subjects included and excluded in the different analysis datasets will be listed.

#### 7.5 Demographic Characteristics and Lifestyle Details

Demographic data (date of birth, sex, race, height [cm], weight [kg] and body mass index [BMI; [kg/m^2]) will be recorded at screening.

Age will be calculated using the following formula:

and will be rounded down to the nearest year (using the SAS Software floor function).

Summary statistics (mean, standard deviation [SD], median, minimum, maximum and number of subjects with an observation [n]) will be presented for age, height, weight and BMI at screening by treatment and overall. The number and percentage of subjects will be presented by treatment for race and sex. The denominator for the percentage is all subjects in the safety population for each treatment. If any values are missing, a "missing" row will be presented on the table.

Lifestyle details (ie smoking history [does the subject smoke, use e-cigarettes or use nicotine replacement products?] and alcohol consumption) will be summarised by treatment and overall.

Demographic and lifestyle data for all subjects will be listed.

#### 7.6 Medical/Surgical History

Medical/surgical history will be recorded for each subject at the screening visit and updated at admission. All medical/surgical history data will be listed by subject.

#### 7.7 Prior and Concomitant Medication

Medications (drug name) will be coded using the World Health Organisation Drug Dictionary Enhanced (WHO DDE) Drug Reference List (2017 version or more recent version) using the following Anatomical Therapeutic Chemical (ATC) classification codes:

- drug name
- preferred name (code)
- therapeutic subgroup (ATC 2nd level code)
- chemical subgroup (ATC 4th level code)

Prior medications are defined as medications that start and stop prior to the first dose of IMP. All other medications will be defined as concomitant medications including those that start prior to first dose of IMP and continue thereafter. Any medications with an unknown start or stop date will be assumed to be concomitant medications unless a partial start or stop date indicates otherwise.

All medications, including coded terms, will be listed. One combined data listing of prior and concomitant medications will be provided. All prior medications as defined above will be flagged with a "#" symbol. Within this flagged group medications that started after screening and stopped before dosing of IMP will also be flagged using a "\*" symbol.

#### 7.8 Other Baseline Characteristics

All other baseline characteristics, as listed below, at screening and on admission (unless otherwise stated) for each period (as appropriate) will be listed by subject for all subjects:

- alcohol breath test
- carbon monoxide breath test
- urine drug screen
- virology (screening only)
- creatinine clearance (screening only)

